Participants will receive a phone call and be asked about adverse events. They will also provide their daily stool chart to assess the severity of the constipation and use of laxatives, softeners, bulking agents and suppositories. *Patients with two or fewer complete, spontaneous bowel movements will qualify for the treatment period. A bowel movement occurring within 24 hours of suppository, softener, bulking agent or enema use will NOT be counted. A spontaneous stool is a stool occurring in the absence of a laxative, softener, bulking agent or suppository.* PAC-SYM and PAC-QOL to be administrated on day 14, or at the clinic at Dose 1 visit the following day if they fail to bring the completed survey.

PERIOD 2.1 (Stage 1): Single dose

Safety, tolerability and pharmacokinetics of orally administered single-dose ENT-01 in Sentinel Group

Duration: 22-57 days

The 10 patients in the sentinel group will be assigned to Cohort 1 and will participate in 8 single dosing periods.

Subjects	D1	D4-8	D7-15	D10-22	D13-29	D16-36	D19-43	D22-50	D25-57
1-2	25mg	50mg	75mg	100mg	125mg	150mg	175mg	200mg	
3-4		25mg	50mg	75mg	100mg	125mg	150mg	175mg	200mg
5-6		25mg	50mg	75mg	100mg	125mg	150mg	175mg	200mg
7-8		25mg	50mg	75mg	100mg	125mg	150mg	175mg	200mg
9-10		25mg	50mg	75mg	100mg	125mg	150mg	175mg	200mg

All 10 patients will be pre-selected in advance of check-in for their first scheduled dosing period. All laxatives, suppositories, softeners, bulking agents and enemas will be disallowed during the 24-hour period before or after the administration of study medication. Patients will wear the I-Button continuously for the entire dosing period. The first two patients (subjects 1-2) will first be admitted and given a single dose. The study will be conducted at a hospital-based clinical unit and patients will be monitored for 24 hours after the dose. Unless there are any safety

concerns, patients will be released at this time and brought back for the next dosing on Day 4-8 (D4-8), after a minimum of a 72 hour observation period. Dopamine will be taken prior to the clinic visit on an empty stomach. Patients will self-administer the study medication during their clinic visit. The dose will be taken on an empty stomach along with 8 oz. of water after baseline observations in the clinic. The patient will not be allowed to ingest any food for at least 60 minutes after study medication.

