
Sleep Assessment: Patients will wear an I-Button continuously from Day 8 of the Run-In Period to Day 5 of the Wash-Out period except during periods of bathing.

Visit Day 1: Informed Consent

The eligible volunteers will be asked to sign the informed consent after explanations of the study and after all their questions have been answered. Patients will be registered to the study after they have provided informed consent.

At the beginning of the run-in period, the new cohort of 40 patients will have a screening visit. In the screening visit inclusion and exclusion criteria will be accurately reviewed and constipation history assessed using the Rome IV criteria. Patients will be included who have been constipated for over 6 months, who have two or fewer complete spontaneous bowel movements per week unresponsive to milk of magnesia and requiring Miralax or another laxative, bulking agent, softener or suppository at least once weekly. Details relating to depression, anxiety, memory problems, hallucinations, loss of smell, voice difficulties and sleep patterns, thrashing and speaking out loud during sleep, swallowing difficulties and dyspepsia will be recorded. Patients will have a physical examination, their vitals will be checked and their past and present medical history as well as their medication intake will be reviewed. Baseline blood chemistry will be checked. Women with childbearing potential will have a negative pregnancy test to enter in the study and within 48 hours of each of the studies. After they have signed the consent form, participants will be scheduled for the study-days and entry into the randomization procedure. They will also be instructed as to the use of daily diaries and I-Buttons. BDI, PFS-16, NMSQ, PDHQ, RBDQ, PDSS, MMSE, UPDRS and Trail-making A and B, PAC-SYM and PAC-QOL will be administered. They will be given Sitzmarks capsules to take on Days 8, 9, and 10.

Day 8, Phone call Assessment of constipation severity off medication and of colonic transit

Daily stool diaries which they will have been filling in for a week will be reviewed and those

patients with two or fewer complete, spontaneous bowel movements per week will proceed to

Sitzmarks assessment. This will trigger shipment of study drug.

Sitzmarks procedure Days 8, 9, and 10:

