• The patient will self-administer the Sitzmarks capsule (contains 24 radiopaque markers; Konsyl Pharmaceuticals, Texas, USA) by mouth with water on Days 8,9, and 10 and will consume their usual diet during this period. The patient will abstain from using suppositories or enemas until they return on Day 11. An abdominal XR will be scheduled on Day 11

Day 11 – Site Visit 2

An abdominal XR will be obtained to determine the location and the extent of elimination

of the radiopaque markers. Patients who expel at least 80% (19 or more of the markers) have

grossly normal colonic transit. If remaining markers are scattered about the colon, the condition is

most likely hypomotility or colonic inertia. If remaining markers are accumulated in the rectum or

rectosigmoid, the condition is most likely functional outlet delay. Radiographs will be collected in

electronic format and subsequently analyzed in blinded manner by a centralized reader ([name] MD, and [name], MHA, Division of Gastroenterology and Hepatology, Mayo

Clinic). The patient will be given study medication (B) and a PAC-SYM and PAC-QOL to take

home. This will trigger randomization to treatment or placebo and to PK or no PK.

Day 14- Phone call

Patients will be asked to complete the PAC+SYM and PAC-QOL questionnaires. They

will be instructed to take the medication the following morning on an empty stomach and not to

eat anything for at least 60 minutes thereafter. Baseline complete, spontaneous bowel movements

(CSBM) will be calculated from the diaries at the 14 day phone call as CSBM/entries x

7.Baseline PAC-SYM and PAC-OOL and baseline ease of passage and consistency will also be

obtained at this time-point.

PERIOD 3.2 (Stage 2): Multiple doses

Safety, tolerability and pro-kinetic effect of orally administered multiple-dose ENT-01 in

Sentinel Group followed by Remaining Cohort

Cohort 2 (40 patients, of which 10 comprise the sentinel group):

Duration: 17-19 days

The purpose of this period is to demonstrate the continued pro-kinetic effect beyond that

of a single-dose, to confirm the effective pro-kinetic dose for each individual and to establish the

safety, tolerability and PK of multiple doses of ENT-01. A pro-kinetic dose is defined as the dose

that results in a spontaneous, complete stool on at least two of the three dosing days. Once the

pro-kinetic dose is established, and assuming there are no safety concerns, each patient will be

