9.5 Clinical Laboratory Procedures

The following tests will be obtained at baseline and at the end of each Period.

- CBC
- Chemistry
- PT/PTT
- Pregnancy test
- Urinalysis

PK Samples for 10 selected subjects:

Timed blood samples (5.0 mL) will be collected into potassium-EDTA treated tubes for analysis of ENT-01 and its metabolite plasma concentrations.

Blood samples for PK analysis will be collected at the following times before and after dosing on the day before randomization and on Day 6 of the randomized period: 0 (pre-dose), 60 min, 2, 4, 8 hrs.

Once collected, PK samples will be stored in a -20°C or -70°C freezer until time of shipment. Labels and appropriate shipping materials will be provided to sites.

The concentration of study drug will be determined from the plasma samples using a validated analytical method. Details of the method validation and sample analysis will be included with the final clinical study report.

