APPENDIX 1: CLINICAL LABORATORY DETERMINATION

Hematology	Serum chemistry	Urine analysis (dipstick)
Full and differential blood count Hematocrit (Hct) Hemoglobin (Hb) Mean corpuscular hemoglobin (MCH) Mean corpuscular hemoglobin concentration (MCHC) Mean corpuscular volume (MCV) Platelet count Red blood cell (RBC) count White blood cell (WBC) count with differential	Albumin Alanine aminotransferase (ALT) Alkaline phosphatase (ALP) Aspartate aminotransferase (AST) Blood Urea Nitrogen (BUN) or Urea Carbon dioxide (CO ₂) Creatinine Creatine kinase and subtypes Electrolytes (Na, K, Cl, Ca, P) Gammaglutamyl transpeptidase (GGT) Glucose Lactate dehydrogenase (LDH)? Total bilirubin Direct bilirubin Total cholesterol Triglycerides	Appearance pH Protein Glucose Ketone bodies Indicators of blood and WBCs Specific gravity Urine human chorionic gonadotropin (HCG) (pre-menopausal females only) Urobilinogen
Coagulation		
Prothrombin time (PT) Activated partial thromboplastin time (PTT)	at will be performed an all female no	

Pregnancy test: A pregnancy test will be performed on all female patients of child-bearing potential at the screening visit.

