APPENDIX 2: SCHEDULES OF EVENTS

STAGE 1

Period	Ru Ser	1 n-In ntinel wks	2.1 Single Dose 3-8 wks	2.2 Wash-Out 2 wks
	D1	D14	D1	
Consent	X			
Demographics	X			
Inclusion/exclusion	X	x		
Medical history	X			
Physical exam	X		X	x
Vital signs ¹	X		X	x
Rome-IV	X			
Blood chemistry	X		х	х
Hematology	X			
Urinalysis	X			х
Fecal occult blood	X		х	х
EKG	X		х	х
Pregnancy test	X			
Monitoring			х	х
Discontinue medications	X			
Re-start medications				х
Diary entries	X	x	х	х
UPDRS	X		X^4	x ²
I-Button ³	X	х	X	
PAC-QOL	X	х	X ⁴	x ²
PAC_SYM	X	X	X ⁴	x ²
RBDQ	X		X ⁴	x ²
NMSQ	х		X ⁴	x ²
PFS-16	х		X ⁴	x ²
UM-PDHQ	х		X ⁴	x ²

BDI	X		X ⁴	\mathbf{x}^2
Trail-making A and B	X		X ⁴	x ²
MMSE	X		X ⁴	\mathbf{x}^2
Adverse events		Х	X	х
PK samples			X ⁵	
Schedule visit days	X			
Administer ENT Dose			X	
Record Medications	X	Х	X	x
Daily phone calls to on non-visit days		Х	X	х

¹Vital signs taken before dose and 2 hours after dose

²End of period 2

³I-Button placed days 9 of run-in periods and worn continuously through day 5 of wash-out periods.

⁴Surveys taken at last dosing visit

⁵PK samples taken pre-dose and 1, 2, 4, 8 and 24 hours post-dose

STAGE 2

		Period 3.1 Run-In					Period 3.2 Multiple Dose		Period 4 domized Treat	ment	Period 5 Wash-Out	
	Day 1 Visit 1	Days 2-7, 9- 10, 12-13 Calls	Day 8 Call	Day 11 Visit 2	Day 14 Call	Days 1-13, 15-16 Calls	Day 14 Call	Day 1 Visit 3 ⁶	Days 2-5 Calls	Day 6 Visit 4	Days 1-7 Calls	Day 14 Visit 5
Informed Consent	X											
Inclusion/Exclusion Criteria	X											
Demographics/Medical History	X											
Prior and Con Meds	X											
Complete Physical Exam	X											X
Height	X											
Weight	X			X				X		X		X
Vital Signs ¹	X			X				X		X		X
ECG	X							X				X
Local Labs - Chemistry, Hematology	X							X		X		X
Local Labs - Urinalysis, Serum Pregnancy	X											
Fecal Occult Blood	X							X				X
Randomization								X				
Study Drug Dispense, Accountability, or Collection				Х				X		X		
Reminder to Begin Taking Study Drug the Next Morning					X							
Instructions to Discontinue Laxatives and other BM Medications	X											
Instructions to Resume Laxatives and other BM medications												X
Stool and Sleep eDiary Instruction/Review	X	X	X	X	X	X	X	X	X	X	X	X
AE Review		X	X	X	X	X	X	X	X	X	X	X
Rome IV questionnaire	X		X									
UPDRS	X							X				X
PAC-QOL and PAC-SYM	X				X		X	X		X		X
Questionnaires - BDI, NMSQ, PFS-16, UM- PDHQ, MMSE, Trail-Making A and B, RBDQ and PDSS	X							X		X		Х

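### The July 2017 schedules mark one pregnancy test, on Day 1, and omit later tests the protocol text asks for; a site following the Stage 2 schedule would X-ray 10 days, and start dosing 14 days, after it

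*Protocol*

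**What the plan says.** The July 2017 protocol deals with pregnancy testing in several places.

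- **Section 3.1**, Visit Day 1, under Period 1 (Stage 1) and again under Period 3.1 (Stage 2a): "Women with childbearing potential will have a negative pregnancy test to enter in the study and within 48 hours of each of the studies". The word *studies* is not defined.
- **Section 9.5**, whose list includes the pregnancy test: "The following tests will be obtained at baseline and at the end of each Period".
- **Appendix 1**: "A pregnancy test will be performed on all female patients of child-bearing potential at the screening visit". Its dipstick panel also lists urine HCG for pre-menopausal women.
- **Appendix 2**: the Stage 1 pregnancy row is marked at run-in Day 1 only. The Stage 2 row, "Local Labs - Urinalysis, Serum Pregnancy", is marked at Day 1 (Visit 1) only. SAP Tables 2 and 3 repeat both.
- **Sections 4.3 and 9.11** require a negative test before entry, which fits all of the above.

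The events that matter are dated as follows. In Stage 2, "An abdominal XR will be scheduled on Day 11" of run-in. After the Day 14 phone call, patients "will be instructed to take the medication the following morning on an empty stomach and not to" eat for an hour, so the first dose is taken at home on Day 15. In Stage 1, two questionnaires may be handed in on Day 14 "or at the clinic at Dose 1 visit the following day if they fail to bring the completed survey", so the first dose is also on Day 15 at the earliest.

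SAP Table 4 gives the Stage 2 schedule under the February 2018 amendment. It marks on-site urine tests at Visit 2 (Day 11), Visit 3 (fixed-dose Day 4) and Visit 4 (wash-out Day 14), and has no X-ray row.

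**The concern.** Site staff usually work from the schedule of events. Here the schedule shows the entry test and none of the later tests in the body text. The first event affected is an abdominal X-ray in Stage 2, and the second is the start of an investigational drug that Section 1.3 describes as being given orally to humans for the first time. Pregnancy is an exclusion criterion, and the later tests are the protocol's own check that it still holds when exposure begins. A site that follows the schedule also collects deviations from Sections 3.1 and 9.5 without knowing it. This is a participant-safety and conduct matter; it does not touch the estimate or test of any endpoint.

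**Working it through.** **1. Tests required by Section 9.5 against tests marked in the pregnancy row** (Day 1 counted as baseline)

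- Stage 2: baseline + ends of Periods 3.1, 3.2, 4 and 5 = 1 + 4 = 5. Marked: 1.
- Stage 1: baseline + ends of Periods 1, 2.1 and 2.2 = 1 + 3 = 4. Marked: 1. (The Stage 1 schedule marks urinalysis again at wash-out, so the dipstick HCG might be done there. In Stage 2, urinalysis shares the row marked only on Day 1.)

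**2. Days from the Day 1 test if only the July 2017 schedules are followed**

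| Event | Day, counted from run-in Day 1 | Gap |
|---|---|---|
| Stage 2, first X-ray | 11 | 11 − 1 = 10 d (240 h) |
| Stage 2, first dose | 14 + 1 = 15 | 15 − 1 = 14 d (336 h) |
| Stage 2, second X-ray, response at first dose level | 14 + (3 + 2) + 6 = 25 | 24 d |
| Stage 2, second X-ray, full 75–175 mg escalation | 14 + (5 × 3 + 4) + 6 = 39 | 38 d |
| Stage 1, first dose (earliest) | 15 | 14 d |

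The second-X-ray rows use 3 days per dose level, 2 to 4 further fixed-dose days, and the X-ray on Day 6 of Period 4.

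**3. What a 48-hour rule would need**

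If *studies* covers the X-ray, a test is needed on about Days 9–11. If it covers the first dose, a test is needed on about Days 13–15. The Stage 2 schedule marks neither.

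**4. What Section 9.5 would add if followed**

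Its end-of-run-in test has no stated visit. Day 14 is a phone call, and the last run-in site visit is Visit 2 on Day 11. If the test is done at Visit 2, before the film, it covers the X-ray and falls 15 − 11 = 4 days before the first dose. If it is done on about Day 14, it falls 1 day before the dose but after the X-ray. The text does not say which. The end-of-Period-4 test falls at about Visit 4, the second X-ray visit, so the 24–38 day figures apply only to a site using the schedule alone.

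**5. Under SAP Table 4**

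Visit 2 test to first dose: 15 − 11 = 4 days, or 96 h, against 48 h. There is no X-ray to cover.

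**The case against.** The strongest reply is that the text already requires the tests, so the gap is a few missing marks in a table. All the statements can be met together: a schedule showing one test does not forbid others. That stands, and it is why this is a low-priority point.

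Second, *studies* may not mean procedures. The protocol calls its two parts the Stage 1 study and the Stage 2 study, and the sentence appears once in each stage's screening paragraph, so it could mean a test within 48 hours of entering each stage. On that reading there is no 48-hour conflict over the X-ray or the first dose. Against it, the next sentence in the Period 3.1 paragraph speaks of scheduling study-days. The Period 2.1 line "The study will be conducted at a hospital-based clinical unit" sits among dosing-session instructions, but it can equally describe Stage 1 as a whole. The wording does not settle the matter. Section 9.5 still asks for tests the schedules omit, whichever reading is taken.

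Third, the exposure is limited. Section 4.3 requires a hormonal method plus a barrier, or a double barrier. Section 1.3 predicts peak plasma levels of about 0.5 ng/ml (25 mg) to 2 ng/ml (200 mg). Stage 2 starts only after safety-board review of Stage 1. With entry ages of 30–86, few women may be of child-bearing potential; the number is not given. These facts lower the risk but do not supply the tests.

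A reader might infer that even full compliance with Section 9.5 leaves the Day 11 X-ray without a recent test. The documents do not support that, because the end-of-run-in test could be done at Visit 2.

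**Conclusion.** The inconsistency holds for the July 2017 protocol. Appendix 1 and both schedules show a test only at screening or Day 1, while Sections 3.1 and 9.5 ask for more. A site using the Stage 2 schedule alone would take the first X-ray 10 days, and start dosing 14 days, after the only marked test. Section 9.5 protects the X-ray only if its end-of-run-in test is placed at Visit 2, which the text leaves open.

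For Stage 2 patients under the February 2018 schedule, most of this is resolved. A reader might infer that Table 4 itself breaches the 48-hour rule by about 2 days (96 − 48 = 48 h). That follows only if the wording survived and refers to dosing. SAP Section 2.1 describes changes to the dose range and the removal of randomization and says nothing else changed, but the amended protocol text is not among the documents.

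The point is worth correcting but minor. It rests on sites working from the schedules and on Day 1 being the baseline test. No endpoint or analysis is affected.

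**What to change.** Define *studies* in both Section 3.1 paragraphs as named time points, and bring Section 9.5, Appendix 1 and both Appendix 2 schedules to the same list. For women of child-bearing potential, mark an on-site negative urine test as follows.

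- **Stage 2:** at Visit 2 (Day 11) before the X-ray; at Visit 3; at Visit 4 before the X-ray, where the randomized period applies; and at the end-of-wash-out visit. State whether the Visit 2 test, about 4 days earlier, is accepted for the first dose.
- **Stage 1:** at check-in before the first dose, at the end of dosing, and at the end of wash-out. State whether the later dosing sessions (up to 8 in all, over 22–57 days) also need one.

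Under the February 2018 schedule, Stage 2 needs no new row; the 4-day gap only has to be accepted or closed.

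The cost is urine kits and a few minutes at existing visits: 4 kits per woman in Stage 2 under the July 2017 design and 3 in Stage 1. The ceiling, if every patient were a woman of child-bearing potential, is 40 × 4 + 10 × 3 = 190 kits; the real number will be lower. Testing at each later Stage 1 session would add at most 10 × 7 = 70. Closing the 4-day gap, if that is preferred, would need a home test or an extra visit, because the Day 14 contact is by phone.

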Forty patients will be screened and included in the study on the assumption that roughly 15% will drop-out, leaving 34 patients who complete the study. Ten sentinel patients will have been pre-selected and ready to go before the study is initiated. Patients who fit the inclusion criteria and who agree to sign an informed consent will be included in the study. At the beginning of the run-in period, they will be asked to stop benzodiazepines and other sedatives, hypnotics, opiates, protein pump inhibitors and all laxatives, bulking agents, softeners and suppositories. They will be allowed to continue antihistamines, anti-cholinergics, anti-psychotics, dopamine and antidepressant medication at stable dose and to use rescue medication for constipation as needed as *long as they note it in the diary.* Patients will remain off these medications throughout the study. Patients who fulfill Rome IV criteria will be included in the run-in period. Patients will be required to be constipated for over 6 months, have two or fewer complete, spontaneous bowel movements per week, unresponsive to milk of magnesia and requiring Miralax or another laxative, bulking agent or softener at least once per week. Rescue medication for constipation will consist of 10mg suppository of Dulcolax, taken if no bowel movement has occurred for three consecutive days. Rescue medication will be taken on the fourth day in the morning. Dulcolax suppository can be repeated up to three times and will be followed by the use of an enema if the Dulcolax was ineffective. BDI, PFS-16, NMSQ, UM-PDHQ, RBDQ, PDSS, MMSE and Trail-making A and B, PAC-SYM and PAC-QOL will be administered. They will keep daily diaries and record stool frequency, consistency, ease of evacuation, completeness and use of suppositories (if it occurs) and various sleep parameters. The diaries will be reviewed daily by the study coordinator to ensure compliance. Patients with two or fewer complete, SPONTANEOUS bowel movements will have the Sitzmarks motility assessment, complete the run-in period and proceed to the treatment period. Bowel movements occurring within 24 hours of a suppository, (or accidentally used laxative, bulking agent, softener) or enema will not be counted. At the end of the first week, assuming they are allowed to proceed to the treatment period, they will also have Sitzmarks motility assessment to assess baseline colonic motility. Symptoms of Parkinson's disease will be assessed using the Unified Parkinson's Disease Rating Scale (UPDRS) during ON states. ON-state will be reached one hour after dopamine intake.

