Patients will be taken off study drug. They will continue to keep a daily diary throughout the period. They will be contacted by phone daily during Week One to check diaries and laxative use. During the first week of the wash-out period they will only use rescue medication as needed. During the second week, they will be restarted on all original medications including laxatives but will continue their diaries until the termination of the study. They will continue to wear the I-Button for the first 5 days of this period. During the last visit, the UPDRS, BDI, Trail-Making A and B, MMSE, PFS-16, NMSQ, UM-PDHQ, RBDQ, PDSS, PAC-SYM and PAC-QOL will be administered

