4.4 Exclusion Criteria

- Unable or unwilling to provide informed consent or to comply with study procedures.
- Diagnosis of secondary constipation beyond that of PD
- Structural or metabolic diseases that affect the GI system
- Functional GI disorder
- Unable to withdraw the following medications 2 weeks prior to the dose-escalation period and throughout the study: Laxatives, opiates, sedatives, hypnotics, protein pump inhibitors or any medications which may cause constipation
- History of recent major surgery (within 60 days of screening)
- Any clinically significant abnormalities on screening laboratories or physical examination requiring further evaluation or treatment.
- Neurological disorder other than PD
- On treatment with intra-jejunal dopamine or carbidopa/levodopa (i.e. Duopa)
- Treatment with COMT inhibitors (entacapone, tolcapone, Stalevo)
- Patients starting a new PD medication or modifying an existing medication within 4 weeks prior to enrollment
- Unable to maintain a stable diet regimen
- Patients with a cognitive impairment that preclude them from understanding the informed consent
- Patients placed under legal guardianship
- Acute GI illness within 2 weeks of the baseline period
- History of major GI surgery (e.g. previous abdominal surgery, including Cholecystectomy), except that patients with uncomplicated appendectomy are allowed.
- ALT or AST > 1.5 X upper limit of normal (ULN) during screening

• Females who are pregnant or breastfeeding

• History of excessive alcohol use or substance abuse

Patient or caregiver unable to administer daily oral dosing.

• Participation in an investigational clinical study within the 6 months prior to dosing in

the present study.

• Any other reason, which in the opinion of the Investigator would confound proper

interpretation of the study.

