4.4 Pharmacodynamic Evaluations

Unless otherwise stated, the following pharmacodynamic (PD) variables are evaluated for both Stage 1 and Stage 2. All PD parameters will be defined for each period. The periods under consideration for summary and analyses are run-in (i.e., baseline), each dosing period or treatment period (as applicable), and washout period (i.e., follow-up period).

For Stage 1 stool diaries, the baseline PD parameters will be calculated using all diaries from run-in period; dosing period PD parameters will be calculated on dosing day immediately following each dose (for CSBM and SBM after dose, need to consider the day before dosing for the rescue medications use); and washout PD parameters will be calculated using diaries excluding the first day diaries (i.e., this one day diaries will be attributed to last dosing period).

For Stage 2 stool diaries, all the diaries for each dosing period will be used for the calculation of PD parameters. The washout period started 24 hours of last dose.

For Stage 1 sleep diaries, PD parameters will be calculated using all diaries from run-in period; up to last dosing period. The first 7-day diaries after last dosing period will be attributed to last dosing period and the second 7-day diaries after last dosing period will be attributed to washout period.

For Stage 2 sleep diaries, PD parameters will be calculated using all diaries from run-in period; all diaries in each dosing period up to last dosing period. The washout period started 24 hours of last dose.

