8 DEFINITIONS AND CONVENTIONS FOR DATA HANDLING

8.1 Definition of Baseline

For all evaluations unless otherwise noted, baseline is defined as the most recent measurement prior to the first administration of study drug in Stage 1. Baseline can be the same date as first dose, given the measurement is expected prior to first dose when only date information is available.

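### Stage 2 mood, fatigue, cognition and hallucination scores have no baseline taken after sedatives and opiates are stopped, so in patients who stop such drugs the change to Visit 3 mixes ENT-01 with the withdrawal

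*Protocol*

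**What the plan says.** **Stopping the drugs.** Protocol 3.1, Period 3.1, says: "At the beginning of the run-in period, they will be asked to stop benzodiazepines and other sedatives, hypnotics, opiates". Protocol 4.4 excludes patients who are "Unable to withdraw the following medications 2 weeks prior to the dose-escalation period and throughout the study". With a two-week run-in, that also points to Day 1. Footnote 5 to SAP Table 4 ties the instruction to Visit 1 and names clonazepam and opiates.

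**Scoring the battery.** The Visit Day 1 entry of Period 3.1 reads: "BDI, PFS-16, NMSQ, PDHQ, RBDQ, PDSS, MMSE, UPDRS and Trail-making A and B, PAC-SYM and PAC-QOL will be administered". In Protocol Appendix 2 the row "Questionnaires - BDI, NMSQ, PFS-16, UM- PDHQ, MMSE, Trail-Making A and B, RBDQ and PDSS" is marked at Visits 1, 3, 4 and 5. The UPDRS row is marked at Visits 1, 3 and 5. Neither is marked on run-in Day 8, 11 or 14. SAP Table 4 (February 2018 amendment) likewise has nothing between Visit 1 and Visit 3. Only PAC-SYM and PAC-QOL are repeated on run-in Day 14, and the protocol takes their baseline there.

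**Baseline and analysis.** SAP 8.1 says "baseline is defined as the most recent measurement prior to the first administration of study drug". That sentence goes on to refer to Stage 1 only, but SAP 4.4 equates baseline with run-in for both stages. Either way, the only pre-dose score for these scales is the Day 1 score. SAP 7.7 and 7.7.1 summarise change from baseline by period, with no formal ENT-01 versus placebo comparison.

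**Last visit.** Protocol 3.1, Period 5, says: "During the second week, they will be restarted on all original medications including laxatives". The battery is repeated at the end of that week.

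**The concern.** SAP 3.2.2 makes sleep, memory, energy, mood, fatigue and hallucinations the Stage 2 exploratory objective. Sedatives, hypnotics and opiates act on the same functions. A before-after comparison without a control can be attributed to ENT-01 only if background treatment is the same at both ends. In patients who entered on one of these drugs it is not: the first score is on usual medication and the second is off it.

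Protocol 4.2 enriches the sample for sleep delay, sleep fragmentation and RBD, and the SAP footnote names clonazepam, so some users are to be expected. A mean change could then be read as a signal for or against ENT-01 when part of it comes from stopping another drug.

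The sleep diary raises a related but weaker question: "For Stage 2 sleep diaries, PD parameters will be calculated using all diaries from run-in period". Its baseline therefore pools the first nights after the stop with later ones.

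**Working it through.** **1. Line up the two timelines** (Protocol 3.1 and Appendix 2; SAP Tables 3 and 4).

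| Time point | ENT-01 | Restricted CNS drugs | Battery scored |
|---|---|---|---|
| Run-in Day 1 (Visit 1) | not started | usual use; told to stop | yes |
| Run-in Days 8, 11, 14 | not started | stopped | no (PAC-SYM and PAC-QOL only, Day 14) |
| Visit 3 | on | stopped | yes |
| Visit 4, ENT-01 arm (July 2017 protocol) | on | stopped | yes, except UPDRS |
| Visit 4, placebo arm (July 2017 protocol) | off | stopped | yes, except UPDRS |
| Wash-out Day 14 | off | documents disagree | yes |

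Between the first and third rows both columns change together for a user, and no score separates them. Visit 3 comes after at least about 14 run-in days + 3 days at the first dose + 2 fixed-dose days = 19 days off the drugs.

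Recall periods strengthen the point. In the protocol appendices PFS-16 asks about two weeks, NMSQ about one month and the UPDRS about one week. At Visit 1 all three look back to a time before the stop.

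**2. Size of the distortion.** Let f be the share who stop a restricted drug and d the average shift caused by stopping. With no ENT-01 effect, mean change = f × d. The documents give neither f nor d, nor the sign of d.

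- PFS-16, assumed f = 20-40% and d = 3-5 points: 0.20 × 3 = 0.6 to 0.40 × 5 = 2.0 points. On the 64-point range (16 to 80, SAP 4.4.3.5) that is 0.6/64 = 0.9% to 2.0/64 = 3.1%.

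**3. What it would do to a test.** Protocol 10.5 names a paired t-test for within-patient change. No power figure is given for these scales. As a check on the method, the protocol's own paired-t figures for colonic transit (SD 22.4 h, 80% power, two-sided 0.05) reproduce with the noncentral t: 11.09 h at N = 34 (stated 11.1) and 10.18 h at N = 40 (stated 10.2).

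Now express d in SDs of the change score and assume no ENT-01 effect. The mean is f·d, the SD is √(1 + f(1−f)d²), and the noncentrality is √N·f·d/SD. For f = 0.3, d = 0.5, N = 34: SD = √(1 + 0.21 × 0.25) = 1.026 and noncentrality = 5.831 × 0.15/1.026 = 0.85, which gives a rejection rate of 13.1%.

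| f (assumed) | d, SD (assumed) | Spurious mean, SD | False positive, N = 34 | N = 40 |
|---|---|---|---|---|
| 10% | 0.5 | 0.05 | 5.9% | 6.1% |
| 20% | 0.5 | 0.10 | 8.6% | 9.3% |
| 30% | 0.5 | 0.15 | 13.1% | 14.7% |
| 30% | 1.0 | 0.30 | 33.9% | 39.1% |
| 50% | 1.0 | 0.50 | 71.6% | 78.8% |

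The SAP, which supersedes the protocol's statistics, lists only descriptive summaries for these scores. Under the SAP the consequence is a biased mean change (third column). The rejection rates show what a reader applying the protocol's test would face.

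**4. Does a run-in repeat cure it?** Mostly. At Day 11, about 10 days after the stop, PFS-16 recall still covers about 14 − 10 = 4 on-drug days and NMSQ, taking a month as 30 days, about 30 − 10 = 20. At Day 14 the figures are about 1 and 17. UPDRS recall would be wholly after the stop.

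**The case against.** The strongest reply is that little rides on this. The endpoints are exploratory, the summaries are descriptive, Trail-making and PDSS are only listed (SAP 4.4.3.10), so MMSE is the only cognitive scale analysed, and every figure for size is assumed. The PFS-16 example is at most about 3% of the scale. All of this stands. It limits the importance of the point but does not separate the two causes of change.

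Three stronger readings are tempting, and the documents do not support them.

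- *A reader might infer that patients are back on sedatives and opiates at the last visit, so an improvement that reverses at wash-out would mimic a drug effect.* That rests on the Period 5 sentence (Period 2.2 has the like for Stage 1). Against it, Period 3.1 and Protocol 4.4 keep patients off throughout, and Protocol 4.6 disallows these drugs and mentions reinstatement only for proton pump inhibitors. Appendix 2 places the resume instruction on Day 14 itself, for bowel medication. SAP Table 4 has a row covering other restricted medications, but its footnote names no sedative or opiate. The background medication at that visit is therefore unsettled.
- *A reader might infer that being on ENT-01 and being off these drugs coincide at every visit.* Under the July 2017 protocol, placebo patients at Visit 4 are off both. That comparison is sound in this respect, but the amendment removed randomisation and the SAP keeps the comparison descriptive because of the small sample.
- *A reader might infer that the sleep diary has the same fault.* Both sides of that comparison follow the stop instruction, and the documents do not say that early run-in nights are disturbed by withdrawal. A sensitivity analysis is as far as this goes.

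It is also fair to object that a Day 11 battery cannot clear the NMSQ recall window. That stands, and it is why a split by drug use is needed as well.

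**Conclusion.** The point holds for the contrast from baseline to Visit 3. For patients who stopped a restricted CNS drug, change in BDI, NMSQ, PFS-16, UM-PDHQ, MMSE, RBDQ and UPDRS cannot be attributed to ENT-01 alone. Patients who took no such drug are not affected.

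The size is f × d, with both terms unknown. It is negligible if few patients take these drugs and material if many do, and it could run for or against ENT-01. It does not follow that an observed improvement would be an artefact.

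The finding rests on the schedule, not on the assumed figures, and it does not depend on how the restart question is resolved. The primary CSBM endpoint uses run-in diaries, and PAC-SYM and PAC-QOL have a Day 14 baseline, so neither is affected in this way. The plan already has a post-withdrawal baseline for those two instruments. Protocol 10.5 also mentions an end-of-run-in comparison for the other scales, for which the schedule collects no scores.

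**What to change.** 1. Repeat the battery after withdrawal at existing run-in contacts: rater-administered scales at Visit 2 (Day 11), and self-completed scales on Day 14 with PAC-SYM and PAC-QOL. Name these scores as the Stage 2 baseline in SAP 8.1. State that PFS-16 and NMSQ recall still reaches into on-drug days.
2. For all patients, including those already enrolled, report change separately by whether a restricted CNS drug was in use at Visit 1. Medication is reviewed at that visit, and prior medication is coded and listed under SAP 7.5, so no new data are needed.
3. Add a sensitivity analysis with run-in nights 8-14 as the sleep-diary baseline. I-Button recording already starts on Day 8.
4. Reconcile Protocol 3.1 (Periods 2.2, 3.1 and 5), 4.4, 4.6, Appendix 2 and SAP Table 4 with its footnotes on whether sedatives and opiates are restarted before the last visit. Until then, do not present wash-out Day 14 scores as an off-ENT-01 comparison on equal background medication.

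Cost: a longer Visit 2 and some added questionnaires on Day 14, seven rather than fourteen baseline nights in one sensitivity analysis, and one extra table.
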